### **Number of subjects:**

Based on published data for children with moderate preschool wheeze it is apparent that approximately five healthcare attendances occur per child per year. In the current study, we wish to reduce the proportion of healthcare contacts by at least one-third per year. In order to achieve this with 80% power, and accepting statistical significance at the 5% level, we require a minimum of 36 evaluable patients with moderate wheeze per group. Evaluable patients are those from whom at least a blood sample to assess inflammation and an oropharyngeal swab to determine infection can be obtained prior to randomisation.

A total of at least 72 children will therefore be recruited. However, this is the minimum number, and we aim to recruit 100 children (50 per group) if possible.

The number of subjects is not based on a precise power calculation as this is a proof of concept study to determine the feasibility of this approach, and to inform a future power calculation for a large multi-centre trial addressing the same question.

**3.1 Study Outcome Measures:** Primary outcome – number of unscheduled healthcare visits in the 4 month intervention period. Secondary outcomes – health related quality of life for the child and family, number of hospitalisations, days of oral steroids.

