## 5. RANDOMISATION AND ENROLMENT PROCEDURE

### 5.1 Randomisation practicalities

All randomisation and enrolment will occur during routine working hours – as all research visits will take place in the Biomedical Research Unit during the week between 9am and 5pm. Children will be recruited when they are clinically well, not during an acute attack.

We will use the Imperial INFORM database Unit to undertake randomisation

We wish to stratify randomisation according to sex and age, to achieve similar numbers of boys and girls in each group, and to have a similar average age for each group.

The age stratification will be as follows: >1-  $\leq$ 3 years and >3 -  $\leq$ 5 years

As wheezing in preschool children is a seasonal disorder (majority of symptoms and exacerbations occur between September – April each year), the baseline assessments and pre-randomisation visits will be arranged between late August – December each year, so that randomisation and intervention take place between September – January each year, to allow the 4 month intervention period to fall within the main season.

All patients will be given a study specific 24hrs emergency contact card immediately after being randomised. The card includes details of the study: Study title, patient trial number, CI/PI's contact details along with out of hours contact details in case of emergency.

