### 8.2 BASELINE ASSESSMENTS

At the clinic appointment parents of eligible children will be approached and will be verbally informed about the study and given a written information sheet. Parents' contact details will be taken and after a few days will be telephoned to ask whether they would like to take part in the study. Once parents have agreed, they will be invited for a research visit for baseline assessments prior to randomisation.

As wheezing in preschool children is a seasonal disorder (main symptoms between September – April each year), the baseline assessments and pre-randomisation visits will be arranged between late August – December each year, so that randomisation and intervention take place between September – January each year, to allow the 4 month intervention period to fall in the main season.

All baseline assessments will be made providing the child has not had any acute wheezing episodes within the last 2 weeks. Also, with their Consultant's permission, parents will be asked to stop administering any regular inhaled steroids (if they have been taking them) for 2 weeks prior to the research visit.

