**8.6 TRIAL CLOSURE**

The minimum number of children to be recruited into each arm is 36, however, as this is a proof of concept study, an accurate power calculation cannot be performed, indeed part of the reason for this study is to determine the size of a larger trial that would be needed to definitively answer whether pathological phenotype based management is superior to current clinical guidelines. Therefore, recruitment of patients will continue until the end of the trial funding period, December 2018.

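### The 80% power claimed for 36 children per group rests on annual visit figures, is never converted to the 4-month primary outcome, and cannot be reproduced from the stated inputs

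*Combined protocol and SAP*

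**What the plan says.** Under Number of subjects in section 3, the protocol takes from a cited source that in moderate preschool wheeze "approximately five healthcare attendances occur per child per year". The aim is to "reduce the proportion of healthcare contacts by at least one-third per year". It continues: "In order to achieve this with 80% power, and accepting statistical significance at the 5% level, we require a minimum of 36 evaluable patients", specified as children with moderate wheeze, per group. The minimum total is 72, with a target of 100 (50 per group) if possible.

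Section 3.1 defines the primary outcome as the "number of unscheduled healthcare visits in the 4 month intervention period".

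The sample-size paragraph ends with a disclaimer: "The number of subjects is not based on a precise power calculation as this is a proof of concept study". Section 8.6 likewise says an accurate calculation is not possible, but repeats the floor: "The minimum number of children to be recruited into each arm is 36".

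On seasonality, section 5.1 says the "majority of symptoms and exacerbations occur between September – April each year", and section 8.2 refers to "main symptoms between September – April each year". Section 9 names Poisson regression for the primary endpoint and allows a t test or Mann-Whitney test for numerical data. The document gives no standard deviation, dispersion, sidedness, 4-month control rate or dropout allowance.

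**The concern.** The rate and the effect are annual, while the trial counts visits for a third of a year. For a count outcome the information depends on the expected number of events. If the calculation used twelve months of visits, the 4-month comparison has much less power than stated, unless most of a child's yearly visits fall inside the intervention window.

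The stake is how the result is read. If the trial closes near 36 per group with no significant difference, a reader will take it that a one-third reduction had an 80% chance of being detected. The trial is also meant to inform the size of a larger one, so its own planning assumptions should be traceable.

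**Working it through.** **Inputs from the protocol.** Control rate 5 per child per year; reduction of one-third (rate ratio 2/3); 5% level; 80% power; 36 per group minimum, 50 per group target; outcome window 4 months; Poisson regression named in section 9.

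**Assumptions made here.** Two-sided test (one-sided shown as a variant); variance equal to the mean (Poisson); the seasonal spreads listed below.

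**Formulas.** With control mean m₁ and intervention mean m₂ = (2/3)m₁ over the window:

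- n per group = (1.960 + 0.842)² (m₁ + m₂)/(m₁ − m₂)² = 7.849 × 15/m₁ = 117.7/m₁
- power = Φ[(m₁ − m₂)/√((m₁ + m₂)/n) − 1.960]

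**Step 1: try to reproduce 36.**

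- Annual Poisson counts, 5 vs 3.33: n = 117.7/5 = 23.5, so 24 per group. Power at 36 is Φ(3.464 − 1.960) = 93%. This does not give 36.
- Annual counts with SD 2.5: n = 2 × 7.849 × (2.5/1.667)² = 35.3, so 36. The SD is not stated.
- Poisson counts over 8 months, 3.33 vs 2.22: n = 117.7/3.33 = 35.3, so 36. This window is not stated and is not the primary outcome.

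So 36 can be reached, but only by adding an input that the protocol does not give.

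**Step 2: apply the 4-month window.**

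| Spread of the five yearly visits | 4-month means | n for 80% | Power at 36 | Power at 50 |
|---|---|---|---|---|
| Even over 12 months | 1.67 vs 1.11 | 71 | 52% | 65% |
| 75% evenly over September–April | 1.88 vs 1.25 | 63 | 56% | 71% |
| All evenly over September–April | 2.50 vs 1.67 | 48 | 69% | 82% |

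For the first row at 36: (1.667 − 1.111)/√(2.778/36) = 2.00, and Φ(2.00 − 1.96) = 0.516. For the last row: 0.833/√(4.167/36) = 2.449, and Φ(0.489) = 0.688.

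**Step 3: what would give 80%.** Solving 117.7/m₁ = 36 gives m₁ = 3.27 visits in four months, and 3.27/5 = 65% of the yearly visits. At 50 per group, m₁ = 2.35, or 47%. The protocol says only that most symptoms fall in an eight-month season.

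**Step 4: sensitivity at 36 per group (even spread; all in season).**

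- One-sided 5%: 64%; 79%.
- 10% dropout (32.4 per group), two-sided: 48%; 64%.
- Mann-Whitney on simulated Poisson counts: about 48%; 66%. At 50 per group: 61%; 79%.
- Overdispersion lowers power further. Its size cannot be derived from the document. As an example, a negative binomial dispersion of 0.5 (variance = mean + 0.5 × mean²) gives about 33%; 40%.

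**Step 5: reduction detectable with 80% power (two-sided Poisson).** At 36 per group: 45% for a control mean of 1.67, 38% for 2.5. At 50 per group: 39% and 32%.

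**The case against.** The best defence is that the protocol calls itself a proof of concept and disclaims a precise calculation twice. It treats 36 as a floor, aims for 100 children and recruits until funding ends. That is fair and limits the seriousness of the point. But the 80% and 5% remain in the text, the number is presented as required for them, and section 8.6 repeats the minimum. A reader cannot tell which statement governs. At 50 per group, power reaches 80% only near the favourable end of the cases shown.

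Second, without a variance the inputs determine no sample size, so 36 cannot be called arithmetically wrong. An annual SD of 2.5 is only modestly above the Poisson value of √5 = 2.24, and it may have come from the cited source. This stands, and the conclusion is therefore that 36 is not reproducible. Even so, an annual SD would leave the mismatch with the 4-month outcome.

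Third, the trial enrols moderate to severe wheezers, who may attend more than five times a year. A 4-month mean of 3.27 would correspond to about 6.5 visits a year if all fell evenly in September to April (3.27 × 2), or 9.8 if spread over the year (3.27 × 3). That is possible, but the protocol plans on five a year and states the 36 for moderate wheeze. If a higher rate was intended, it needs to be given. It is also unclear whether the five attendances include scheduled ones; that could move power either way.

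Finally, the paragraph speaks of reducing a proportion. A fall from 67% to 33% would need 35 per group, close to 36. But no baseline proportion is given, and the primary outcome is a count.

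**Conclusion.** The concern holds. The stated power is justified on a window three times as long as that of the primary outcome, with no conversion, and 36 per group cannot be derived from the inputs given. Taking the protocol's five visits a year, Poisson variance and a two-sided 5% test, power at 36 per group is about 52% with an even spread and 69% with all visits spread evenly over September to April. Neither is a bound: more visits concentrated in the window, or a higher attendance rate, would raise power, while overdispersion or dropout would lower it. The 80% holds at 36 under Poisson only with a 4-month control mean of about 3.3, which the protocol does not document. Given the proof-of-concept status and the disclaimers, this is a statement that should be corrected rather than a flaw that invalidates the design.

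**What to change.** Choose one of the following for the sample-size paragraph in section 3, and keep section 8.6 consistent with it.

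1. Remove the statement that 36 per group gives 80% power, and justify the number on feasibility and on informing the later trial.
2. Restate it on the 4-month count with the control rate, variance and sidedness. For example: *Assuming Poisson counts, a two-sided 5% test and a 4-month control mean between 1.67 (five visits a year, evenly spread) and 2.5 (all in September to April), 36 per group gives about 52% to 69% power for a one-third reduction, and 50 per group about 65% to 82%. With 80% power the detectable reduction is about 45% to 38% at 36 per group and 39% to 32% at 50. Overdispersion or dropout would lower power.*
3. If the 80% is kept, give the SD or time window that was used and show how it applies to the 4-month count, or give the data supporting a 4-month control mean of about 3.3.

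The cost is rewording one paragraph. No extra patients are needed and the conduct of the trial does not change. Under options 1 and 2 the stated power becomes less favourable or is dropped.

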#### **4. PARTICIPANT ENTRY**

Patient recruitment at a site will only commence once the trial team has ensured that the following approval/essential documents are in place:

1. The main REC, and Clinical Trial Authorization (CTA) approval,
2. Final sponsorship and/or R&D approval (NHS Permission),
3. Sponsor has conducted the trial initiation procedure

Patient identification will take place at up to 5 sites (Royal Brompton Hospital, Kings College Hospital, Chelsea & Westminster Hospital, St Mary's Hospital and Hillingdon Hospital, London), all research visits, screening assessments, randomisation and drugs will be dispensed from the Brompton Hospital only. Kings College Hospital, Chelsea & Westminster Hospital, St Mary's Hospital and Hillingdon Hospital will be used as patient identification (PIC) sites.

All sites participating in the trial will also be asked to provide a copy of the following:

1. Host site (R&D approval) and/or NHS Permission

All subjects who wish to enter the study will be fully screened and consented by the Chief Investigator, or one of the qualified clinicians involved in the study as Clinical Co-investigator.

##### **4.1 Pre-randomisation Evaluations**

All participants will undergo an initial research / screening visit which will involve the following tests:

Full blood count and Vitamin D

Total serum IgE and RASTs to house dust mite, grass pollen, tree pollen, cat, dog, aspergillus, milk, egg, peanut

Assessment of lung function by incentive spirometry and lung clearance index (LCI) using the multiple breath washout technique  
Exhaled nitric oxide – using the offline tidal breathing technique  
Sputum induction using nebulised hypertonic saline  
Oro-pharyngeal swab  
Symptom questionnaire  
Health related quality of life questionnaire  
[Urine sample for cotinine levels \(and for storage if parents consent\)/salivary cotinine](#)

#### **4.2 Inclusion criteria**

Age  $\geq$  1 years, <6 years  
Reported recurrent wheeze, needing at least 2 admissions +/- oral steroids in the last 12 months, at least one admission +/- oral steroids in the last 6 months

Past wheeze confirmed by a clinician

#### **4.3 Exclusion criteria**

Any known cardiac disease  
Any chronic respiratory condition (other than preschool wheeze) diagnosed by a physician  
Any chronic condition that increases susceptibility to respiratory tract infections such as severe developmental delay and feeding difficulty / unsafe swallow  
Prematurity  $<34$  weeks, or requirement of ventilation in the newborn period  
History of neonatal chronic lung disease  
Family not contactable by telephone

#### **4.4 Withdrawal criteria**

The trial will be analysed using an intention to treat approach.  
The intervention arm or taking part in the trial will not affect the acute management of the child in any way, should the child become ill or develop symptoms, they should be taken to be seen by a healthcare professional in the usual way. Management of any acute episodes will not be influenced by the study or study team in any way. If during the 4 month intervention period the child's clinicians / healthcare workers suggest a change in the maintenance therapy is needed, then this will be undertaken without any negotiation. The study team will request that they are informed of the change, and the child will still be included in the analysis because of the intention to treat design.  
If the participants wish to withdraw consent to take part in the study, the data obtained until the time of withdrawal will be used – as it is an intention to treat analysis – providing the participants agree. If however they do not wish for any of the data to be used or analysed, then all data will be destroyed. Parents / families will be free to withdraw at any stage, and that will not impact in any way on their child's routine clinical management.

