**8.5 LOSS TO FOLLOW-UP**

All attempts will be made to stay in touch with families, initially weekly phonecalls will be undertaken during the intervention period to stay in touch, and subsequently, even if they do not wish to attend the hospital for follow-up visits, information will be obtained by phone call about symptoms, medication and unscheduled healthcare visits. If a family cannot be contacted, the GP and local hospital will be contacted to determine any change of address.

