## **9.0 STATISTICS AND DATA ANALYSIS**

Categorical data will be presented as number and percentage and comparisons between groups done using the chi squared or Fishers exact test. All numerical data will be tested for normality and normally distributed data will be presented as mean  $\pm$  SD and comparisons between groups done using the 2 sample independent t test. For the data that are not normally distributed the median (IQR) will be presented and comparisons between groups done using the Mann-Whitney test. Poisson regression will be done to determine the factors that affect the primary endpoint, the number of unplanned hospital visits.

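### A withdrawn family's visit count stops early but enters a fixed 4-month primary outcome, and the planned between-arm tests ignore time observed

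*Combined protocol and SAP*

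**What the plan says.** - **Outcome.** Section 3.1 defines the primary outcome as the "number of unscheduled healthcare visits in the 4 month intervention period": a count over a window of fixed length.
- **Withdrawal.** Under section 4.4, if the family agrees, "the data obtained until the time of withdrawal will be used", and the reason given is intention to treat. The only alternative offered is destruction of all the child's data. There is no option to stop taking part while allowing a records check at month 4.
- **Analysis.** Section 9 uses a two-sample t test for normally distributed data. Otherwise, "For the data that are not normally distributed the median (IQR) will be presented and comparisons between groups done using the Mann-Whitney test". A Poisson regression is added to find factors that affect the primary endpoint. The section names no offset, no rule for incomplete follow-up and no sensitivity analysis.
- **Loss to follow-up.** Section 8.5 plans weekly calls, and telephone collection of visits from families who will not attend. For the rest, "If a family cannot be contacted, the GP and local hospital will be contacted to determine any change of address". Nowhere does the plan obtain visit counts from GP or hospital records.

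**The concern.** Withdrawal before month 4 lowers a raw count mechanically. A child who leaves in week 3 with no visits so far would be analysed alongside children who had no visits in 4 months. Keeping that child in the denominator preserves the randomised groups on paper, but does not supply the outcome that section 3.1 defines.

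Two things are at stake. If the amount or timing of withdrawal differs between arms, the arm that loses more child-time appears to do better. If loss is equal, the comparison is not shifted but both mean counts are too low. The trial exists partly to supply figures for a larger one (Study Summary, Aims; section 8.6), so understated visit rates could carry over into that calculation.

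**Working it through.** **Inputs from the plan (section 3, Number of subjects).** Control rate: "approximately five healthcare attendances occur per child per year". Target: "reduce the proportion of healthcare contacts by at least one-third per year". Arm sizes: a minimum of 36 and an aim of 50 per group. The plan gives no withdrawal rate, so the rates below are assumptions.

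**The plan's own figure.** The plan states 36 per group for "80% power, and accepting statistical significance at the 5% level". With n = (1.960 + 0.842)² × (λ1 + λ2)/(λ1 − λ2)²:

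- annual counts, 5 v 3.33: 7.849 × 8.333/2.778 = 23.5, so 24 per group
- 4-month counts, 1.667 v 1.111: 7.849 × 2.778/0.3086 = 70.6, so 71 per group

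Neither gives 36. A comparison of annual means does so with an SD of 2.5, which the plan does not state. Section 3 itself says that the number is not a precise power calculation. That is a separate matter, and 36 and 50 serve below only as arm sizes.

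**Step 1: one child.** At a constant rate, expected visits = 5 × (months observed)/12.

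- Guideline-arm child, full 4 months: 5 × 4/12 = 1.67
- Same child, leaving after 2 months: 0.83
- Same child, leaving after 1 month: 0.42
- Child with the targeted one-third reduction, full 4 months: 1.67 × 2/3 = 1.11

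An untreated-rate child who leaves halfway therefore scores below a fully observed child in whom the targeted effect is achieved.

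**Step 2: arm ratio.** Let a share w withdraw at times uniform over the window. Each leaver is observed for half of it on average, so the arm's mean count is multiplied by 1 − w/2. The raw ratio is the true ratio × (1 − w1/2)/(1 − w0/2), where w1 is loss in the phenotype arm and w0 in the guideline arm.

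| Assumed loss, phenotype v guideline | Multiplier | Raw ratio, no effect | Raw ratio, true 0.667 |
|---|---|---|---|
| 10% v 5% | 0.95/0.975 | 0.974 | 0.650 |
| 20% v 5% | 0.90/0.975 | 0.923 | 0.615 |
| 30% v 10% | 0.85/0.95 | 0.895 | 0.596 |
| 5% v 20% | 0.975/0.90 | 1.083 | 0.722 |
| equal | 1 | 1.000 | 0.667 |

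**Step 3: equal loss.** At 15% in both arms each mean is multiplied by 1 − 0.15/2 = 0.925, a fall of 7.5%. The control mean drops from 1.67 to 1.54, or 0.125 visits.

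**Step 4: error rate.** This was simulated with Poisson counts, no true effect, 20% v 5% loss, a leaver's observed fraction uniform from 0.05 to 1, and 4,000 runs (Monte Carlo standard error near 0.3 to 0.4 percentage points).

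| Per group | Poisson, no offset | Mann-Whitney | Poisson with offset |
|---|---|---|---|
| 36 | 7.2% | 6.8% | 5.5% |
| 50 | 8.9% | 8.1% | 4.8% |

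With the offset the mean estimated ratio returned to 1.00 under no effect, and to 0.66 when the truth was 0.667.

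**Step 5: size against noise.** Assume negative binomial counts with mean 1.67, dispersion k = 1.5 and 50 per group. The standard error of the log ratio is √[2 × (1/1.667 + 1/1.5)/50] = 0.225. The shift at 20% v 5% is |ln 0.923| = 0.080, or 0.36 standard errors. At 10% v 5% it is 0.026, or 0.12 standard errors. The 0.125-visit fall in Step 3 compares with a standard error of the arm mean of √[(1.667 + 1.667²/1.5)/50] = 0.27.

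**The case against.** **The plan never says that a partial count is scored as complete.** That stands as a matter of wording. A reader might infer a stated scoring rule, but this follows only from the methods. A t test or Mann-Whitney on raw numbers can do nothing else. A Poisson regression could take an exposure term, but none is stated, and it is described as a search for influencing factors, not as the between-arm comparison.

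**The rule covers withdrawal of consent only.** This stands too. For families who are simply lost no scoring rule is written. That their partial counts enter is an inference from intention to treat and the weekly collection of visits.

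**Outcome collection is stronger than the address-tracing sentence suggests.** Families who cannot be reached by telephone are excluded at entry (4.3). Weekly calls record visits (section 3). The month-4 visit asks for the whole-period count (8.4), and families who will not attend can give visits by telephone (8.5). A traced family can then be asked. So the reading that anyone who stops attending is undercounted is not supported. The residue is families who withdraw consent, or stay untraceable, within 4 months.

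**Differential loss is speculative.** Correct. A reader might infer that the phenotype arm will lose more families and so gain apparent benefit, but nothing in the documents shows this. Sections 4.4 and 11.3 keep children whose treatment is changed in the study, and section 5.2 describes parents as unaware of allocation.

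**The effect is small for a proof-of-concept trial.** Largely fair: Step 5 puts it well under one standard error. It is still a systematic shift that a larger trial would inherit, and it is cheap to remove.

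**Consent for records access may already exist.** The consent pages were not available for review, so no claim is made that it is missing.

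**Conclusion.** The point holds for families who withdraw consent within 4 months and, by inference, for those who remain untraceable. For them the plan brings a truncated count into a fixed-window outcome and compares arms by methods that ignore time observed. This is more than missing detail, because following the text as written produces the undercount.

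The size is modest and conditional. The arm ratio is biased only when the amount or timing of loss differs by arm: 0.97 to 0.89 under no effect across the assumed excess losses in the phenotype arm, and above 1 if the guideline arm loses more. Equal loss leaves the ratio unbiased and lowers both means, by 7.5% at an assumed 15%. All of this rests on assumed withdrawal rates, uniform leaving times and a constant visit rate. The simulated error rates also assume no overdispersion; with it, the same bias is a smaller share of the standard error. The documents do not establish that the result will be biased, or in which direction. Nor do they say that the follow-on trial will be sized from an unadjusted mean, only that this trial is to inform its size. The change should be made, but it does not threaten the design.

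**What to change.** 1. **Section 9.** Make the between-arm comparison of the primary outcome a count regression (Poisson with robust standard errors, or negative binomial) with treatment arm as covariate and log(time observed) as offset. It should replace the t test or Mann-Whitney on raw counts. An offset added only to the existing exploratory Poisson regression would leave the problem where it is. Record the date last observed for every child, and report visit rates per child-time for use in sizing the next trial.
2. **Assumptions.** State that the offset assumes leaving is unrelated to visit rate and that the rate is roughly constant over the window. The second is doubtful: section 5.1 describes a September to April season, and a 4-month window that opens in January ends in May. Add a simple sensitivity analysis, such as letting the visit rate in the unobserved remainder be lower or higher than the arm's observed rate.
3. **Sections 8.5 and 4.4, subject to consent.** Widen the GP and local hospital contact so that it also collects the number and dates of unscheduled visits up to month 4. Add a middle option for a withdrawing family: stop taking part, but allow this records check. First see whether the consent form already permits it.

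The cost is one date field, one model term, a longer question in a contact already planned and possibly one consent line. Some families may decline, and records may miss some contacts. The offset therefore remains necessary even with the records check.
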